4.2 Sub-Studies

Accompanying substudies, including quantitative, qualitative and economic evaluations, are described in detail below.

4.3 Primary and secondary outcomes

4.3.1 Primary Outcome for main HIVST versus SOC CBDA intervention

The primary outcome is: Comparison between randomisation arms in coverage of recent (within the last 12 months) HIV testing among adult (16 years and above) village residents 12 months after the initiation of the intervention.

A related pre-specified analysis is to compare between randomisation arms the coverage of ever (lifetime) HIV testing among adult (16 years and above) village residents.

These analyses will be based on household surveys carried out in the pre-defined evaluation villages in each randomisation arm.

4.3.2 Secondary Outcome for main HIVST versus SOC CBDA intervention

The secondary outcome is: Comparison between randomisation arms of ART initiation rates for adult (16 yrs or older) cluster residents, during months 1 to 12 of intervention.

This analysis will be based on data extraction from routine ART clinic records. Residential address will be used to identify all new initiations among adults (16 years or older) living within the the wider CBDA catchment area relating to that clinic.

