4.1 Main trial

The main study will be a cluster-randomised trial in up to 5 high HIV prevalence districts (provisionally Blantyre, Machinga, Mwanza, Neno and Thyolo) that already have community-based reproductive health services provided by PSI under funding provided by the German Technical Cooperation Agency (GTZ). This programme supports volunteers to socially-market reproductive and child health products in villages, with products stored and managed by collaborating primary care clinics.

Figure 4. Schematic illustration of Standard of Care and HIVST intervention clusters intervention provided by village-based CBDAs.

Unit of randomisation is the Primary Care + ART Clinic (black cross) and surrounding catchment area villages (large circles with feed-in arrows) to clinic. CBDAs in the HIVST Arm villages will be trained to provide HIVST services as well as reproductive health services (**small solid circles**). CBDAs in the SOC Arm villages will remain with reproductive health services only (**small open circles**). Two separate units of evaluation will be pre-defined before randomisation: one or two evaluation villages that will have baseline-final household surveys, and a wider catchment area including all villages with CBDA activities.

The unit of randomisation will be the **primary care clinic**. The **unit of evaluation** will be defined by **clinic records of adult ART initiations** from villages within the wider CBDA catchment area, and through household survey of **1 to 2 evaluation villages** contained within the catchment population (Figure 5).

The trial will compare **population-level uptake of ART** (as defined by ART clinic records of new initiators listing study villages as their home address) and **coverage of recent HIV testing** (as defined by household surveys) between two arms:

- 1. **Intervention arm**: Addition of HIVST kits, with brief training and IEC material, to the products carried by PSI-supported reproductive health CBDAs, or
- 2. **SOC arm**: CBDAs will continue to offer reproductive health services, but without the addition of HIVST kits

Figure 5. Trial timelines

In a **second-stage randomisation arm**, villages included in the HIVST intervention will be further randomised to

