5.4 Intervention procedures and process evaluation

5.4.1 Intervention procedures

CBDAs linked to PHC clinics allocated to the intervention arm will be provided with training in HIVST and IEC materials including flipboards, used kits to show clients how to interpret positive, negative and inconclusive results, a cotton bud and vial of water to demonstrate the mouth swabbing and development process, leaflets and a buffer stock of OraQuick ADVANCE HIV I/II test kits, to be stored in a locked container in their own home.

Adult (16 years or older) participants wishing to know their status will be provided with brief pre-test counselling together with the kit, and an envelope containing a self-completed

questionnaire for return of the used test, a telephone hotline number, a self-referral slip for the nearest PHC offering ART services in case of a positive result, and information on how to access VMMC for HIV-negative men. The kit contains instructions for use and results interpretation in Chichewa.

Clients will be encouraged to return their used kits confidentially to the CBDA, either in person or by posting in the sealed envelope into an opaque locked "ballot box" container kept in the counsellor's house. Clients will also be encouraged to seek post-test advice from the CBDA, which can be "generic" (i.e. not results based) or results-based.

Kits will be replaced by the PHC clinic supervisors on presentation of used kits, and following inspection of an HIV test logbook to confirm recording of names and addresses, but not results, of clients. Numbers of used kits, and results on late re-read, will be recorded by the CBDA/PHC supervisor. HIVST logbooks will be kept at the CBDAs home in a locked container.

There are no sharps or hazardous materials.

Couple's testing will be encouraged. In the case of couples wanting to self-test together, both partners will be asked to attend the IEC session, but clients will also be allowed to take up to 2 kits home if the partner cannot attend.

Testing of children (aged 15 years or less) will not be permitted as part of this trial, but can be arranged through special arrangement with the PSI Supervisors. For CBDAs participating in the **Home-initiation Arm** of the second stage randomisation, additional training will be provided on how to advise the client about the availability of this option, and the need to share a provisionally positive HIVST result in order to access this option.

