5.6.4 Outcome evaluation

For the comparison of **coverage of recent** / **ever HIV testing**, outcomes will be evaluated through household surveys as detailed above.

For evaluation of **ART initiations within study area villages**, maps showing study area boundaries and names of participating villages will be produced and displayed in HCT and ART clinics. ART register completion will be adjusted in collaboration with MoH to allow previous HIVST / home-initiation episodes to be documented in the "Comments" column.

Clinic staff will be asked to ensure that all clients are asked directly if they are attending following HIVST results and that the village of residence is clearly recorded in the ART register. The self-referral cards, which are presented by the participants to the clinic, will contain spaces for ART clinic staff to log confirmatory results, the national ART number for clients entering HIV care, and any other relevant referrals (e.g., VMMC).

PSI CBDA supervisors will extract these data on a monthly basis from each of the 20 ART clinics included in the study. Retrospective data extraction will also be used to provide an indication of pre-intervention ART initiations from the 20 study clinics.

In **Home-Initiation villages**, where participants have the option of requesting home initiation of care, PSI CBDA supervisors will fill out HIV care registration cards and maintain a logbook allowing cross-reference by ART number with the local ART clinic. Total numbers of clients confiding positive HIVST results will be recorded by all CBDAs in post-test logbook recording disclosure and other referral events without name.

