5.8.4 Outcomes

Overall numbers of ART initiations per 1,000 total adult population will be calculated for each clinic during months 1 to 12, and will be compared between intervention and control arms after adjusted for any major imbalance between the trial arms in factors such as pre-intervention ART initiation rates.

The proportion of residents accepting HIV testing will be estimated both overall and within sex, age and village strata, using population denominators from the post-intervention household prevalence survey. Participant characteristics during different time periods of the study will also be compared.

Estimates of linkage into newly accessed care will be assessed using the referral completion rate. This will compare the number of participants who disclosed positive results to CBDAs during a specific period of time to the number of participants accessing confirmatory testing following HIVST over the same time period.

The number of new HIV-positive cases will be ascertained through re-reading of returned kits and participants sharing results with CBDAs.

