9.3. HTC and HIVST

All individuals selecting to self-test will be offered pre- and post-test information and referral to the most convenient clinic offering ART services. Participants will also be given the opportunity to discuss any fears about the process or results prior to testing and to disclose their status and receive advice and support for post-test services.

Participants are not required to disclose the results of HIVST to the distribution agent, but such will be encouraged so that they can receive results-based, post-test information. The only exception is during the pilot accuracy study, where self-testing will need to be disclosed in order to verify the accuracy of HIVST results against confirmatory results.

All disclosed HIV status results will remain confidential.

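### As worded, the secondary ART outcome can omit a cluster resident's start at another study clinic while keeping that resident in the denominator, and the protocol's definitions of the outcome are not reconciled

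*Protocol*

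**What the plan says.** The secondary outcome of the main trial (Protocol 4.3.2) is "Comparison between randomisation arms of ART initiation rates for adult (16 yrs or older) cluster residents, during months 1 to 12 of intervention". The same section takes the events from routine ART clinic records and uses residential address to pick out adults "living within the the wider CBDA catchment area relating to that clinic". Section 5.8.4 gives the calculation: "Overall numbers of ART initiations per 1,000 total adult population will be calculated for each clinic during months 1 to 12".

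Section 4.1 describes the same outcome differently, "as defined by ART clinic records of new initiators listing study villages as their home address", and does not limit it to the clinic of the person's own cluster.

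On data collection, section 5.6.4 asks clinic staff to record village of residence in the ART register and states that "PSI CBDA supervisors will extract these data on a monthly basis from each of the 20 ART clinics included in the study".

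On referral, section 5.4.1 gives each self-tester "a self-referral slip for the nearest PHC offering ART services in case of a positive result". Section 4.1 (Arm 1B) also refers to the nearest ART clinic, and section 9.3 promises "referral to the most convenient clinic offering ART services". None of these names the cluster's own clinic as the destination.

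Section 5.2.1 asks that the wider catchment (10 to 20 villages) avoid District boundaries and major alternative ART providers, but only where this can be achieved. Two stricter criteria, that the clinic be the village's dominant ART source and that villages be well separated, are listed for the one or two evaluation villages.

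**The concern.** The outcome is meant to describe residents of a cluster. Sections 4.3.2 and 5.8.4 build it clinic by clinic, each register being matched to that clinic's own catchment. The numerator then depends on where a resident chose to start treatment, while the denominator does not.

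The evaluation-village criteria do not cover most of the villages that generate this outcome, so some starts at a neighbouring study clinic are to be expected. HIVST referral operates in one arm only. It could therefore change where residents start ART as well as how many start. An analysis that cannot separate the two could misstate the effect on ART demand, which is the trial's one named secondary outcome for the main comparison.

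**Working it through.** **The wordings side by side.** Take a resident of cluster A who starts ART at study clinic B.

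| Rule | Counted in A? | Counted in B? | In A's denominator? |
|---|---|---|---|
| 4.3.2 with 5.8.4, register by register | No | No | Yes |
| 4.1 (study-village address), credited to the clinic attended as 5.8.4 may suggest | No | Yes | Yes |
| 4.1, credited to the cluster of residence | Yes | No | Yes |

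Only the third row matches an outcome about cluster residents. No section states it.

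**Inputs.** The protocol gives about 62,500 adults in 20 catchments, so 62,500 / 20 = 3,125 per cluster on average. It gives no ART initiation rate, no expected effect on ART, and no share of starts made at the own clinic. There is thus no stated figure to reproduce for this outcome; the sample size in 7.2 concerns the primary outcome only. Everything below is assumed unless marked as from the protocol.

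**Effect on the rate ratio.** Let s0 and s1 be the shares of residents' starts made at the own-cluster clinic under standard of care and HIVST. Under the narrow rule:

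observed ratio = true ratio × s1 / s0

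With a true ratio of 1.50:

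- s0 = s1 = 0.80: 1.50 × 0.80 / 0.80 = 1.50. Events are lost; there is no bias.
- s0 = 0.90, s1 = 0.85: 1.50 × 0.85 / 0.90 = 1.42.
- s0 = 0.90, s1 = 0.80: 1.50 × 0.80 / 0.90 = 1.33.
- s0 = 0.80, s1 = 0.90: 1.50 × 0.90 / 0.80 = 1.69.

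**What those shares imply.** Per 100 usual starts, a ratio of 1.50 adds 50 HIVST-prompted starts. Suppose usual starts behave alike in both arms.

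- For s1 = 0.80 with s0 = 0.90, own-clinic starts must total 0.80 × 150 = 120. Usual starts supply 90, so the extra 50 supply 30: 40% of the extra starts occur elsewhere, against 10% of usual starts.
- With 5% of usual and 20% of extra starts elsewhere, the ratio is (95 + 40) / 95 = 1.42.
- In the other direction, with s0 = 0.80 and every extra start at the own clinic, the ratio is (80 + 50) / 80 = 1.63. Reaching 1.69 requires the intervention also to bring some usual starts back to the own clinic.

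**Illustrative power.** Assume a standard-of-care rate of 10 per 1,000 per year, a true ratio of 1.50, 10 clusters per arm, 3,125 adults each, and k = 0.25 borrowed from the primary outcome. On the rate scale, SE² = [r0/3,125 + r1/3,125 + k²(r0² + r1²)] / 10, with a noncentral t on 18 degrees of freedom.

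- No loss (rates 0.010 and 0.015): SE = 0.00168, difference / SE = 2.97, power 0.80.
- 10% loss in both arms (0.009 and 0.0135): power 0.79.
- s0 = 0.90, s1 = 0.80 (0.009 and 0.012): SE = 0.00144, difference / SE = 2.08, power 0.50.

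At assumed rates of 5 and 20 per 1,000 the three values are 0.70, 0.68, 0.40 and 0.86, 0.85, 0.58. Equal loss costs little; unequal loss can matter.

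**The case against.** The strongest reply is that the narrow reading is not the only one. Section 4.3.2 opens with cluster residents and speaks of identifying all new initiations by address. Because the clinic with its villages is the randomised unit, the per-clinic rate in 5.8.4 may simply mean per cluster. Section 4.1 contains no own-clinic limit, and no sentence says that cross-clinic starts are discarded. This stands in part: such starts would be recorded and recoverable, so the protocol does not show that they are lost. But the qualifier in 4.3.2 reads more naturally as a register-by-register match, and nothing assigns a start at another study clinic to the home cluster.

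It can also be said that catchment selection will usually make the nearest clinic the cluster's own. That is fair, and it limits the likely number of crossings. It does not remove them, since the condition on the wider catchment is only a preference.

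A reader might infer that the rule must pull the ART comparison towards no effect, because only HIVST clients receive the referral. The documents do not support this. Standard-of-care residents may also start anywhere. The slip to the nearest clinic could raise the own-clinic share. In Arm 1A, home-initiated clients receive a follow-up appointment at the ART clinic (5.4.1) and are cross-referenced by ART number with the local one (5.6.4), which could also raise it.

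Finally, allocation of register rows is often left to an analysis plan. Here, however, the protocol states a counting rule, in two forms that do not agree, so the point goes beyond absent detail.

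**Conclusion.** The point holds as an unreconciled outcome definition. Sections 4.3.2 and 5.8.4, as worded, can omit a resident's start at another study clinic while that resident stays in the denominator; section 4.1 would include it. Some cross-clinic starts are plausible given the referral wording and the soft condition on the wider catchment.

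The size cannot be derived from the protocol. If own-clinic shares are equal between arms, only events are lost. If they differ by 0.10, as in the scenarios of 0.90 against 0.80 and the reverse, a true ratio of 1.50 is seen as 1.33 or 1.69. These shares, the true ratio and the power inputs are assumptions, and the direction is open. The matter concerns the secondary ART outcome only; the primary outcome comes from household surveys and is unaffected.

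**What to change.** Replace the numerator rule with one based on residence, for example: *new ART initiations among adults aged 16 or older recorded at any of the 20 study clinics, assigned to the cluster of the recorded village of residence whichever clinic was attended, divided by the adult population of that cluster's wider catchment.* Use the same definition in sections 4.1, 4.3.2 and 5.8.4. Report the number and share of cross-clinic starts by arm, and keep the own-clinic count as a sensitivity analysis.

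The cost is a wording change and one matching step against a combined village list. No new data source is needed, since supervisors will already "extract these data on a monthly basis from each of the 20 ART clinics included in the study". The small downside is that similar village names in different catchments must be told apart, for example by District. Starts at clinics outside the study remain missed, and the report should say so.

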4.3.3 Second stage randomisation: home-based versus facility-based assessment for HIV care

Villages in the HIVST intervention area will be randomised to either **HIVST only**, or to **HIVST plus offer of home assessment and HIV care initiation** (first assessment and first 14 days of HIV care medications) with this additional intervention aimed at facilitating linkage into care.

The **primary outcome** for this second-stage randomisation will be comparison between randomisation arms of number of adult (16 yrs or older) village residents disclosing a positive results to the CBDA during months 1 to 12 of intervention, with a confidential post-test log book used to capture these data.

The **secondary outcome** for this second-stage randomisation will be comparison between randomisation arms of ART initiation rates for adult (16 yrs or older) village residents during months 1 to 12 of intervention, with ART clinic records used for this assessment.

4.4 Study population and timeline

Phase 1 of the study is funded from 1st Sept 2015 to August 2017. A second two-year funding phase has been requested, and will if successful allow continuation of the implementation and research. The decision on Phase 2 funding will be made in April 2017.

The main study population will be adults living in selected evaluation villages located within the 5 Southern Districts that have an existing reproductive CDBA programme (Blantyre, Machinga, Mwanza, Neno and Thyolo).

20 Primary care clinics that are actively participating in PSI-CBDA scheme and have an active ART clinic will be selected, with preference given to sites with evidence of high HIV burden in surrounding villages (based on ANC clinic data).

Selection of 20 to 40 evaluation villages for the purposes of household surveys will be based on distance from the primary care clinic (aiming for sites that are at least 10km away), plus considerations affecting ease of access and follow-up. Ideal villages will have an active CDBA volunteer, an adult population of greater than 250, with no alternative HIV care facility nearby, and with no major access problems during the rainy season. If necessary, 2 villages will be selected from any given primary care clinic catchment area to meet the requirement for 250 adults evaluated.

Additional populations will be included for the purposes of the formative studies, the interviews with policymakers, and the VMMC mobilisers.

- 1. Formative studies will include initial cognitive interviews with a convenience sample of up to 144 participants attending routine HTC clinics, to establish ability to understand and follow the new instructions for use before moving into the village residents
- 2. HIVST ICE materials will be piloted for accuracy and acceptability in 2 nonintervention villages within the intervention Districts
- 3. Policymakers and opinion leaders on HIV testing will be included in key informant interviews aiming to support scale up of HIVST if these evaluation studies are promising
- 4. Mobile VMMC clinics operate in overlapping districts and sites to the main cluster randomised trial. The initial evaluation of adding HIVST to VMMC mobilisers will be carried out within the catchment area of the study primary care clinics. However, if results are promising then the intervention will be extended to all PSI VMMC clinic sites, which include other districts.

5. Methods

HIVST will use the OraQuick ADVANCE Rapid HIV-1/2 Antibody Test. The kits, which are manufactured by Orasure, contain the HIVOFT kit, stand, buffer solution, IFUs, materials on counselling and linkage to care, and primary and secondary packaging.

A toll-free telephone number will also be provided with the HIVST kit, which can be used to access verbal pre-test information, test instructions, and results-based post-test information. Participants will also be given information on the nearest clinic for confirmatory testing and ART initiation.

The kits will be distributed for free across all of the distribution models. All distributors will receive a training package in HIVST promotion and support that has been developed in consultation with MoH HIV Department.

The study has four main phases:

- 1. Formative studies
- 2. Piloting in non-intervention area 2 villages
- 3. Cluster enumeration in all 20 ART clinics and evaluation villages
- 4. Intervention and outcome evaluation

5.1 Formative studies and piloting

Formative studies are intended to

- Establish ability to follow HIV implementation the instructions-for-use and confirm high accuracy of supervised HIVST in rural settings
- Inform our understanding of needs through key informant interviews with stakeholders working in HIV policy, product regulation and HIV implementation

5.1.1 Cognitive interviews

Convenience sampling will be used to recruit clients from VCT clinics for the cognitive interviews (PS101A). Eligibility criteria include clients who are 16 years or older, and willing to provide written informed consent for participation in the study. A witnessed thumbprint will be sufficient for those who are unable to read or write. Participants will be purposively selected to ensure a range in location and literacy level.

Four to 12 participants will be recruited for each iteration of the cognitive interviews, with a maximum of 12 iterations of adaptation and trial of the intended IFUs (n = 144). Cognitive interviewing and iterative adaptation will continue until saturation occurs and no further modifications to user materials are made.

